6.2 Primary Endpoint

Change in CFR and HMR measurements at 4 months post CS Reducer implantation compared to baseline

6.3 Secondary Endpoints

- Change in CCS angina class
- Change in the score of all 5 domains of the Seattle Angina Questionnaire for assessing quality of life
- Change in the consumption and frequency of short acting nitrates (spray or sublingual tablets)
- Change in EBEST parameters at 4 months compared with baseline (total exercise duration, time to 1 mm ST segment depression, evidence of ischemia, peak exercise stage, peak exercise diastolic function and filling pressures as measured by echocardiographic E/e', and exercise-induced symptoms)

- Procedural-related Major Adverse Cardiac Events (MACE) defined as: death, myocardial infarction, perforation of the CS, CS total occlusion, or need for urgent dilatation of the Reducer within 4 months of follow-up

7- Study Population:

Patients with chronic refractory angina (CCS class II-IV), no obstructive CAD (<50% stenosis in epicardial vessels and/or iFR>0.89 or FFR>0.8 in vessels with 50 to 70% stenosis), and documented CMD (CFR≤2.5 and/or HMR≥2.5) & or coronary blood flow (CBF) response to acetylcholine ≤ 50%. on clinically indicated coronary angiography and invasive coronary reactivity testing which uses Adenosine, Acetylcholine & Nitroglycerin as standard clinical practice

7.1 Inclusion Criteria:

- Age ≥ 18
- Able to provide written informed consent and willing to participate in all required study follow-up assessments
- Symptomatic CAD with refractory angina defined as CCS class II to IV, despite optimal tolerated medical therapy for more than 3 months.
- Abnormal coronary microvascular function indices: CFR≤2.5 and/or HMR≥2.5 & or coronary blood flow (CBF) response to acetylcholine ≤ 50%.

7.2 Exclusion Criteria:

- Recent (within 3 months) acute coronary syndrome
- Recent (within 6 months) percutaneous coronary intervention revascularization by stent
- Patients with prior coronary artery bypass surgery

- Unstable angina (recent onset angina, crescendo angina, or rest angina with ECG changes) during the last 30 days
- Subjects in cardiogenic shock (systolic pressure < 80mm/Hg, on vasopressors or intraaortic counter pulsation) at the time of consenting. Subjects who recover from cardiogenic shock by the time of consenting are eligible.
- Obstructive CAD on coronary angiography (>70% stenosis or 50-70% stenosis with $iFR \leq 0.89$ or $FFR \leq 0.8$ in epicardial artery)
- Inability to perform invasive coronary flow evaluation and/or measure CFR and HMR in the LAD
- Severe valvular heart disease
- LVEF<30%
- Decompensated congestive heart failure (CHF) or hospitalization due to CHF during the last 3 months
- Patient with a pacemaker electrode in the CS
- Mean right atrial pressure >15 mmHg
- Anomalous or abnormal CS anatomy (e.g., tortuosity, aberrant branch, persistent left superior vena cava (SVC) as demonstrated on angiogram
- CS diameter at the site of planned implantation greater than 13mm or less than 9.5 mm as measure by angiogram
- Severe chronic obstructive pulmonary disease (COPD) indicated by a forced expiratory volume in one second that is less than 55 percent of the predicted value
- Tricuspid valve replacement or repair
- Chronic renal failure (serum creatinine >2mg/dL), and or on chronic hemodialysis
- Moribund, or with comorbidities limiting life expectancy to less than one year

- Known severe reaction to required procedural medication
- Known allergy to stainless steel or nickel
- Magnetic Resonance Imaging (MRI) within 8 weeks of Reducer implantation
- Participation in another ongoing investigational trial
- Additional factors deemed unsuitable for trial enrollment per discretion of principal investigators
- Inmates

7.3 Subject Recruitment, Enrollment and Screening:

The first six patients will be sequentially enrolled, and subsequent enrollment will be held until one-month follow-up. Provided there are no safety concerns at this time, enrollment will continue. Staggered enrollment will help ensure that subsequent patients are not enrolled until there is adequate follow-up and safety of initial patients. The patients for this study will be recruited through the outpatient clinics in the Department of cardiology, including the Chest Pain and Coronary Physiology Clinic and the Coronary Artery Disease Clinic at Mayo Clinic. There have been over 35,000 patients seen in the Cardiovascular Division at Mayo Clinic yearly. There are over 6,000 cardiac catheterizations performed yearly in the cardiac catheterization lab. As a part of our clinical practice, patients with angina referred to the catheterization laboratory for a clinically indicated coronary angiography and found to have non-obstructive CAD are undergoing a comprehensive coronary reactivity testing including assessment of microvascular function with CFR and HMR. Typically, 8-10 patients per month undergo this comprehensive coronary physiology study. This will be mediated through referring physicians. Patients that meet inclusion and exclusion criteria will be considered for recruitment in the study.

7.4 When and How to Withdraw Subjects:

Subjects will be withdrawn from the study prior to completion of all study related procedures if 1 of 5 consecutive patients have serious adverse safety events.

7.5 Data Collection and Follow-up for Withdrawn Subjects:

Even though a subject has withdrawn from the study, it may be important to collect some follow-up or survival data on such subjects throughout the protocol defined follow-up period. Such data is important to the integrity of the final study analysis since early withdrawal could be related to the safety profile of the study device and/or implantation procedure. If a subject withdraws consent to participate in the study, for subject safety reasons, we will make attempts to obtain permission to collect follow up information whenever possible.

[figure not shown]

Figure 3: Flow chart of the study design. CAD: coronary artery disease; CMD: coronary microvascular dysfunction; CRT: coronary reactivity testing; CFR: coronary flow reserve; HMR: Hyperemic microvascular resistance; CCS: Canadian cardiovascular society; SAQ: Seattle angina questionnaire; EBEST: Exercise bike echocardiographic stress test.

8- Study Device, Implantation Procedure, and Subject Compliance Monitoring

8.1 Study Device:

The Neovasc Reducer™ System (Neovasc Inc., Richmond, B.C., Canada) is a stainless-steel mesh pre-mounted on a customized hourglass shaped balloon catheter, is designed to create a focal narrowing in the lumen of the CS to generate a pressure gradient across it ⁴² (Figure 4).

When inflated, the expanded balloon gives the metal mesh its final hourglass configuration.

The narrowing within the CS, and the pressure gradient across the device are established 4–6 weeks after implantation, when the metal mesh should be covered by tissue ingrowth. The semi-compliant delivery balloon is available in one single size, and the final expanded diameters are dependent on the inflation pressure. The proximal and distal portions of the device are configured to different diameters, based on balloon expansion, allowing the device to conform to the tapered configuration of the anatomy of the CS, with a central narrowing of 3 mm in diameter.

Importantly, since the narrow central part of the device is not in direct contact with the vessel wall, and does not cause any vessel wall injury, there is no trigger for tissue growth at this point, and therefore, the vessel lumen at the center of the device remains patent. Moreover, acceleration of venous blood flow through the narrowed center of the device prevents thrombosis at that site.

[figure not shown]

Figure 4: Neovasc Reducer™ System. A) Coronary sinus Reducer pre-mounted on the Reducer Balloon. B) Expanded Reducer over the Reducer Balloon.

8.2 Implantation Procedure:

The Reducer is implanted in the CS through a 9F guiding catheter from the right (or left) internal jugular vein as was previously described⁴². Use instructions of the Neovasc Reducer System and implantation procedure steps are detailed in the accompanying confidential ‘Instructions For Use’ document. In brief, the Reducer system is advanced over a wire inside a 9 F guiding catheter and located within the designated implanting location. When proper location is confirmed, the guiding catheter is withdrawn, exposing the Reducer, which is held in the landing zone previously identified. The balloon is inflated to 4–6 atm to achieve 10–20% oversize of the vessel. Oversizing is important and helps to achieve two goals: (1) to

anchor into the elastic vessel wall to help prevent migration and (2) to trigger a process of injury-induced tissue proliferation ⁴³⁻⁴⁵.

8.3 Subject Compliance Monitoring:

There will be no assessment of compliance as the device will be implanted in the cath lab, and there are no further drugs that need to be administered.

9- Coronary Reactivity Testing

A full clinically indicated coronary flow evaluation will be performed in the left anterior descending artery (LAD) as standard of care to determine study eligibility using an intracoronary combined Doppler-flow and pressure wire (ComboWire XT, Philips Volcano Corporation, Del Mar, California) that provides iFR/FFR, HMR and CFR measurements. In cases in which assessment cannot be performed in the LAD, coronary reactivity testing may be done in the left circumflex (LCx) artery. In brief, after engaging the coronary artery of interest with a guiding catheter, FFR or iFR will first be done in case of moderate (>50 to <70%) epicardial disease to document non-obstructive CAD (FFR>0.8 or iFR>0.89) as was previously described in section 2.4. In cases of mild (<40%) epicardial disease by angiography, FFR/iFR is not recommended but may be done at the discretion of the operator. After confirming non-obstructive epicardial CAD (no CAD, mild CAD<40% or negative FFR/iFR for moderate CAD >50 but <70%), the ComboWire XT will be inserted and parked in the mid LAD for measurement of CFR and HMR. Intracoronary bolus injections of incremental doses (36, 60 and 72 µg) of adenosine will be administered until maximal hyperemia is achieved or the largest dose was given ¹¹. CFR will be measured as the average hyperemic blood velocity post adenosine/average baseline velocity. Highest achieved CFR

will be used for analysis. A cine image of the LAD will be obtained after each adenosine administration. Coronary artery diameter will then be measured offline by an independent investigator in the segment 5 mm distal to the tip of the pressure-flow wire with a quantitative coronary angiography program (Medis Corp, Leiden, the Netherlands) as described previously^{46, 47} and coronary blood flow (CBF) will then be calculated from the Doppler-derived time velocity integral and vessel diameter, where $CBF = \pi \times (\text{coronary artery diameter}/2)^2 \times (\text{average peak hyperemic velocity}/2)$ ⁴⁸. HMR will then be calculated as distal coronary pressure divided by coronary blood flow at maximal hyperemia. For binary analysis, CMD will be defined as $CFR \leq 2.5$ and/or $HMR \geq 2.5$ ^{11, 12, 20, 21}.

10- Prior and Concomitant Therapy

CS Reducer is being tested as an add-on therapy for ANOCA patients with microvascular dysfunction and ongoing refractory angina despite optimal tolerated conventional medical therapy. Any previously ongoing therapy for CMD or other conditions, prior to CS Reducer implantation, can be continued during the study.

11- Study Procedures

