	
 • Inability to perform invasive coronary flow evaluation and/or measure CFR and HMR in the LAD • Severe valvular heart disease • LVEF<30% • Decompensated congestive heart failure (CHF) or hospitalization due to CHF during the last 3 months • Patient with a pacemaker electrode in the CS • Mean right atrial pressure >15 mmHg • Anomalous or abnormal CS anatomy (e.g., tortuosity, aberrant branch, persistent left superior vena cava (SVC) as demonstrated on angiogram • CS diameter at the site of planned implantation greater than 13mm or less than 9.5 mm as measured by angiogram • Severe chronic obstructive pulmonary disease (COPD) indicated by a forced expiratory volume in one second that is less than 55 percent of the predicted value • Tricuspid valve replacement or repair (tissue or mechanical) • Chronic renal failure (serum creatinine >2mg/dL), and or on chronic hemodialysis • Moribund, or with comorbidities limiting life expectancy to less than one year • Known severe reaction to required procedural medication • Known allergy to stainless steel or nickel • Magnetic Resonance Imaging (MRI) within 8 weeks of Reducer implantation • Participation in another ongoing investigational trial • Additional factors deemed unsuitable for trial enrollment per discretion of principal investigator • Inmates
Primary endpoint	Change in CFR and HMR measurements at 4 months post Reducer implantation compared to baseline

Secondary endpoints	
 • Change in CCS angina class • Change in the score of all 5 domains of the Seattle Angina Questionnaire for assessing quality of life • Change in short acting nitrates (spray or sublingual consumption frequency • Change in EBEST parameters at 4 months compared with baseline (total exercise duration, time to 1 mm ST segment depression, evidence of ischemia, peak exercise stage, peak exercise diastolic function and filling pressures as measured by echocardiographic E/e', and exercise-induced symptoms) • Procedural-related Major Adverse Cardiac Events defined as: death, myocardial infarction, perforation of the CS, CS total occlusion, or need for urgent dilatation of the Reducer within 4 months of follow-up

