2.2 Coronary microvascular dysfunction: Symptoms and adverse outcomes

Coronary microvascular dysfunction contributes to myocardial perfusion abnormalities and ischemia ⁵ and leads to poor outcomes. In addition to disabling angina and severely limited quality of life ³, CMD has been associated with a 6-fold increase in adjusted mortality and higher risk of major adverse cardiovascular events (MACE), including diastolic heart failure, acute coronary syndrome, myocardial infarction, and sudden cardiac death ⁵⁻¹⁰.

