² *One subject experienced a migration post-implantation. The Reducer was noted to have moved during insertion but was inflated. As a result, the position of the deployed Reducer device was more proximal than desired. The dislodged Reducer then migrated and a 2nd Reducer was implanted without complications*

³ *Seven subjects were not implanted – 2 for CS dissection, 2 for tortuous anatomy, 1 for CS too small, 1 for inability to advance the guiding catheter, and 1 for movement of the Reducer while retracting the guidewire*

Accordingly, in this Phase-1 study we aim to evaluate the feasibility of CS Reducer implantation and its efficacy on invasively assessed microvascular function in ANOCA patients with CMD.

4- Study Hypothesis

In patients with ANOCA and invasive evidence of CMD, CS Reducer implantation is safe and will improve microvascular function as measured by CFR and HMR.

5- Aims

- 5.1 To evaluate the potential efficacy of CS Reducer implantation in ANOCA patients with CMD on microvascular function using invasive CFR and HMR assessments
- 5.2 To evaluate the potential efficacy of CS Reducer implantation in ANOCA patients with CMD on angina severity and frequency as assessed by CCS angina class and short-acting nitrates use, ischemia and exercise capacity as assessed by exercise bike echocardiographic stress test (EBEST), and quality of life as assessed by SAQ score.
- 5.3 To evaluate the potential efficacy of CS Reducer on left ventricular diastolic function and filling pressures as assessed by transthoracic echocardiographic parameters at peak exercise
- 5.4 To confirm the safety and feasibility of CS Reducer implantation patients with ANOCA and invasively documented CMD.
- 5.5 A successful demonstration in the proposed trial that CS Reducer implantation can be beneficial to patients with CMD will significantly advance the field of research aimed at FDA approval of the CS Reducer for treatment of ANOCA patients with CMD and opening the door to commercialization of CS Reducer for treatment of CMD, which is a critical unmet clinical need. If successful, the next stage of investigation will be the conduct of one or more pivotal registration studies to support FDA approval, and the proposed trial will provide information necessary to design these studies.

6- Study design

6.1 General Study Design:

- Prospective, single center, open label, single arm, clinical trial
- Number of participants: 30 subjects
- Duration of study: 4 months

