Contemporary overall rates of major complications (death/ myocardial infarction/ stroke/ unplanned coronary bypass grafting/ pericardial effusion) related to diagnostic cardiac catheterization procedures at our institution are extremely low (<1 per 1000 left heart catheterization)⁴⁹. Second, coronary reactivity testing is a safe procedure with <1/100 risk of severe adverse events (coronary artery dissection and myocardial infarction)⁵⁰. Third, in the largest available database (REDUCE study), CS Reducer implantation procedure was also shown to be a safe procedure with no CS perforations, cardiac tamponade, peri-procedural

death or myocardial infarction reported in the largest database available at 14 months median follow-up ⁴¹. Lastly, exercise testing may pose a minimal risk to patients if they were to develop arrhythmias during the testing. This risk is minimal, and the room in which EBEST is performed, and personnel performing testing will be equipped to handle any potential complications.

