13.12 Sponsor-Investigator reporting: notifying the Mayo IRB

The sponsor-investigator will report to the Mayo IRB any UPIRTSOs and Non-UPIRTSOs according to the Mayo IRB Policy and Procedures. All serious adverse events must be reported in writing to both the Institutional Review Board by the investigator himself as institutional policies mandate. The investigator must then provide a summary describing the SAE in detail and his assessment of how related the event is to the study device. The documentation related to the SAE must follow the initial SAE report immediately as available. As new information becomes available to the investigator, the investigator must continue to collect and forward this information, and provide a corresponding follow-up summary.

Information collected on the adverse event worksheet (*and entered in the research database*):

- Subject's name:
- Medical record number:
- Disease/histology (if applicable):
- The date the adverse event occurred:
- Description of the adverse event:
- Relationship of the adverse event to the research (device, procedure):
- If the adverse event was expected:
- The severity of the adverse event: (use a table to define severity scale 1-5)
- If any intervention was necessary:
- Resolution: (was the incident resolved spontaneously, or after discontinuing treatment)
- Date of Resolution:

The sponsor-investigator will review all adverse event reports to determine if specific reports need to be made to the IRB and FDA. The sponsor-investigator will sign and date the adverse event report when it is reviewed. For this protocol, only directly related SAEs/UPIRTSOs will be reported to the IRB.

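### The only defined safety endpoint leaves open whether a judgement of cause decides if a death or infarction counts as MACE, and which procedure is meant

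*Combined protocol and SAP*

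**What the plan says.** Section 6.3 gives the last secondary endpoint as "Procedural-related Major Adverse Cardiac Events (MACE) defined as: death, myocardial infarction, perforation of the CS, CS total occlusion, or need for urgent dilatation", counted over 4 months. The synopsis has the same qualifier: "Procedural-related Major Adverse Cardiac Events defined as: death, myocardial infarction, perforation of the CS, CS total occlusion", and so on. It is the only safety item in either endpoint list. Section 11.1 mentions primary safety endpoints, but none is defined anywhere.

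Section 6.1 describes the design as "Prospective, single center, open label, single arm, clinical trial", with "Number of participants: 30 subjects". Aim 5.4 is "To confirm the safety and feasibility of CS Reducer implantation patients with ANOCA" and invasively documented CMD.

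On attribution, Section 13.12 requires the investigator to send the IRB a summary of each serious adverse event with "his assessment of how related the event is to the study device". The worksheet in the same section records the relationship to device or procedure. The opening of Section 13 refers to events needing adjudication but describes no process. Section 13.14 sets up a three-member independent DSMB to review adverse events and the stopping criteria.

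Section 12 contains no safety analysis. Its only population is patients who completed every study procedure and all follow-up.

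**The concern.** If procedural-related is a filter, the MACE count depends on a judgement for which the plan gives no criteria, no time rule and no named classifier. Two features of the trial make that judgement hard.

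- **Competing causes.** Section 2.2 links CMD itself to infarction and sudden cardiac death, and says "CMD has been associated with a 6-fold increase in adjusted mortality". Section 8.1 says the narrowing and pressure gradient are established 4 to 6 weeks after implantation. An infarction at Day 60 could therefore be put down to the device, to the underlying disease or to neither, and none of these is plainly the procedure.
- **More than one procedure.** Section 13.1 treats catheterization, Reducer implantation, reactivity testing and exercise testing as separate sources of risk. It says "coronary reactivity testing is a safe procedure with <1/100 risk of severe adverse events", naming coronary dissection and infarction. That test is repeated at Day 120 (Section 11.7). Whether an infarction caused by it counts is not stated.

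With no control arm and very few events to be expected, the reading chosen may determine the reported safety result.

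**Working it through.** **Step 1. What the text settles.**

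| Question | What the documents give |
|---|---|
| Is the list restricted to events judged related? | Section 6.3 and the synopsis can be read either way |
| Which procedure? | Not stated; Section 13.1 names several |
| Who classifies an event for this endpoint? | No one is assigned. The investigator judges device relatedness for IRB reports (13.12); the DSMB reviews adverse events and stopping criteria (13.14) |
| When does the window end? | 4 months (6.3, 13.4). The repeat test is at Day 120 ± 14 (11.7), so as late as 120 + 14 = Day 134 |
| Who is analysed? | Only patients completing everything (12) |

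**Step 2. Size of one attribution decision.** The plan states no expected MACE rate, safety margin or interval method, so there is no figure of its own to reproduce. Inputs: n = 30 (Section 6.1), assuming 30 attempted implants; x is the number of patients with an event. Exact (Clopper-Pearson) 95% limits are

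- lower = Beta quantile(0.025; x, n − x + 1), taken as 0 when x = 0
- upper = Beta quantile(0.975; x + 1, n − x)

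For x = 0 the upper limit is 1 − 0.025^(1/30) = 11.6%. For x = 1 the lower limit is 1 − 0.975^(1/30) = 0.08%.

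| Count | Rate | Exact 95% CI |
|---|---|---|
| 0/30 | 0% | 0% to 11.6% |
| 1/30 | 3.3% | 0.08% to 17.2% |
| 2/30 | 6.7% | 0.8% to 22.1% |

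**Step 3. Effect of the completers-only rule.** Suppose one patient dies at Day 60 and no other event occurs. Counting all events in all patients gives 1/30. Under Section 12 as written, that patient cannot complete the Day 120 procedures and is not analysed. The result is 0/29, with upper limit 1 − 0.025^(1/29) = 11.9%, even if the death is judged procedure-related. The same would apply to a coronary sinus injury that aborts the implant. Table 2 shows that this can happen: 7 of 211 patients in REDUCER-I were not implanted, two of them for coronary sinus dissection.

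**Step 4. How often one event would be the whole result.** The true 4-month rates below are assumptions. P(at least one) = 1 − (1 − p)^30 and P(zero or one) = (1 − p)^30 + 30p(1 − p)^29.

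| Assumed p | At least one event | Zero or one event |
|---|---|---|
| 0.5% | 14.0% | 99.0% |
| 1% | 26.0% | 96.4% |
| 2% | 45.5% | 87.9% |
| 5% | 78.5% | 55.4% |

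At the lower rates the trial will almost always see no event or one, so one classification can be the entire endpoint result.

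**The case against.** The strongest reply is that the sentence may simply define the term: any listed event within 4 months is a procedure-related MACE. No section says that a causality judgement removes a death or infarction. This stands, and the defect is therefore ambiguity. A reader might infer that an unblinded causality judgement decides whether a death appears in the safety result; the documents do not say so. Nor can Section 13.12 be used to show it, because that text concerns device relatedness in reports to the IRB, not classification of this endpoint. The filter reading is still plausible, since the protocol filters by relatedness elsewhere: the stopping rule counts events attributed to the device (13.14), and one sentence in 13.12 limits IRB reporting to directly related events, although 16.1 says all serious adverse events are reported.

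Second, nothing disappears from the record. Adverse events are defined irrespective of cause (13.2), death and infarction are serious without any relatedness condition (13.3), and all events must be recorded (13.10). This also stands. What is exposed is the endpoint count.

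Third, independent review exists. The DSMB reviews adverse events, but no section gives it the classification of MACE.

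Fourth, coronary sinus perforation, coronary sinus occlusion and urgent Reducer dilatation leave little room for dispute about cause. The question of attribution falls mainly on death and infarction.

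Fifth, the arithmetic is what any reclassified event does at n = 30, the intervals overlap widely, and the 6-fold mortality figure is relative, with no baseline rate or time horizon. All true. The documents do not show that background deaths or infarctions are likely within 4 months.

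Finally, calling the assessment unblinded adds little in a single-arm trial with no allocation to conceal. A bias in the sponsor-investigator's favour is a possibility that the documents do not demonstrate.

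**Conclusion.** The concern holds as an ambiguity in the endpoint, made worse by the analysis population. The plan does not say whether attribution filters deaths and infarctions, whether the Day 120 repeat test is a procedure for this purpose, or who decides. One such decision may move the reported result between 1/30 (3.3%, 0.1% to 17.2%) and 0/30 (0% to 11.6%). Separately, the completers-only rule would turn a death before the Day 120 visit into 0/29 (0% to 11.9%) whatever the attribution, so rewording the endpoint alone would not secure the count.

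The figures assume 30 attempted implants and no other losses. How often the issue would arise depends on an event rate that the documents do not give. The safety record itself is not in question, and no sample-size figure is in dispute.

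**What to change.** - **Section 6.3 and synopsis.** Count any death, myocardial infarction, coronary sinus perforation, coronary sinus total occlusion or urgent Reducer dilatation, regardless of judged cause. Count from the implant attempt through completion of the Day 120 visit, including its ± 14-day window and the repeat test. Use all patients with an attempted implant as the denominator, with exact 95% CIs.
- **Attribution.** Tabulate it beside the count as implant procedure, device, Day 120 test, underlying disease or other, using written criteria and reviewed by the existing DSMB. A procedure-related count can still be read from this table.
- **Section 12.** State that the completers-only rule does not apply to safety.
- **Tidying.** Define or delete the primary safety endpoints mentioned in Section 11.1, and reconcile the IRB reporting statements in 13.12 and 16.1.

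The cost is a few sentences and one added DSMB task. The events and their judged relationship to device or procedure are already collected; the worksheet needs only the finer attribution categories. The downside is that the headline MACE rate may be slightly higher, because background events count.
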